#### **Study Assessments**

Assessments for safety, efficacy, and PK will be performed according to the schedule of events.

##### Safety Assessments

Safety assessments will include AEs, serious AEs (SAEs), DLTs, physical examinations, vital sign measurements, clinical laboratory tests, ECGs, and treatment discontinuation due to toxicity. The AE-reporting period begins with the initiation of study drug and continues through 3 months after the last dose of study drug. All AEs that occur in treated patients during the AE-reporting period specified in the protocol must be reported to the Sponsor, whether or not the event is considered related to study drug. Any known untoward event that occurs beyond the AE-reporting period that the Investigator assesses as related to study drug should also be reported as an AE.

Adverse events will be assessed by the Investigator using the NCI CTCAE, version 4.03.

##### Efficacy Assessments

Efficacy assessments include disease response and progression per PCWG3 and RECIST v1.1, duration of response, and survival.

All patients must have imaging within 28 days before their first dose of study drug as follows: bone scintigraphy and computed tomography (CT) scan of chest/abdomen/pelvis or magnetic resonance imaging (MRI), if indicated. Additional body sites should be imaged as clinically indicated (e.g., neck). Patients with skin, subcutaneous, or lymph node metastases may also have tumor evaluations (including measurements, with a ruler) by means of physical examination.

Patients will undergo CTT1057 PET or 68GaPSMA-11 PET during Screening and at the time of first tumor assessment (week 6-7, 1 week prior to C2D1 dose of CTT1403).

Tumor measurements and disease/composite response assessments, as described above, are to be performed at screening (within 28 days before the first dose of study drug); after every third cycle (ie, within 7 days before Day 1 of Cycle 2, and of every 9 weeks thereafter until development of PD; and at the EOT visit (for subjects who discontinue the study for reasons other than PD).

To accommodate early flare phenomena, the appearance of 2 new lesions on the first bone scan performed after treatment is insufficient to warrant treatment discontinuation. Instead, to document disease progression, 2 additional lesions would need to be observed on a subsequent follow-up scan performed 6 weeks or longer after the first scan.

Patients who discontinue from the study will be assessed for clinical evidence of disease progression (for patients who discontinued for reasons other than PD) every 90 days until up to 6 months after their last dose of study drug.

Measurements of PSA in blood will be performed on Day 1 and 29 of each 8-week treatment cycle, then every 4 weeks thereafter until radiographic or clinical disease progression.

##### Pharmacokinetic and Dosimetry Assessments

Blood samples for assessment of PK parameters for CTT1403 and SPECT/CT imaging for organ dosimetry determination will be collected from all patients treated in the dose-escalation period of the study according to the detailed schedule.

CTT  
CTT1403 Phase 1

Pharmacokinetics and Dosimetry Schedule for Cycle 1

Cycle	Day	PK Collection Timepoint	Blood/Urine Sample	SPECT/CT for Organ Dosimetry
Cycle 1 (6 weeks)	Day 1	•Timepoints after END of infusion: ○ 30 minutes (min) ± 5 min ○ 2 hours ± 30 min		•Timepoints after infusion: ○ 2 hours (± 30 minutes)
	Day 2	24 hours (± 12 hours) after infusion		24 hours (± 12 hours) after infusion observed in prior SPECT
	Day 3	72 hours (± 12 hours) after infusion		72 hours (± 12 hours) after infusion observed in prior SPECT
	Day 8	168 hours (± 24 hours) after infusion		168 hours (± 24 hours) after infusion observed in prior SPECT
	Day 15	336 hours (± 24 hours) after infusion		

**Statistical Methods**

Randomization: No randomization will be utilized in this study.

Safety

Demographics (e.g., gender, age, race) and baseline characteristics (e.g., ECOG performance status, height, weight, and previous prostate cancer therapy) will be summarized with descriptive statistics. Treatment-emergent AEs (TEAEs) through 30 days after last dose of study drug will be summarized by MedDRA version 20.0 system organ class and preferred term. The incidences and percentages of patients experiencing each AE preferred term will be summarized with descriptive statistics. Adverse events will also be summarized by NCI-CTCAE version 4.03 grade and by causality (attribution to study treatment). Dose-limiting toxicities, Grades 3 and 4 AEs, SAEs, and AEs resulting in dose modification or treatment discontinuation will be summarized by preferred terms.

Incidences of laboratory abnormalities will be summarized with descriptive statistics. Vital signs and physical examination results will be summarized with descriptive statistics.

Efficacy

Efficacy parameters will be defined for all patients and for the Dose Expansion cohort.

The primary efficacy endpoint for Dose Expansion is the composite response rate. Composite response rate is defined as the proportion of patients achieving an objective radiographic response by RECIST 1.1 criteria and/or PSA decline > 50% from baseline.

Duration of radiographic response (DoR) is defined as the time from the date measurement criteria are first met for partial response (PR) or complete response (CR) to the date measurement criteria are first met for PD. Radiographic PFS is defined as the time from the date of initiation of treatment to the date measurement criteria are first met for radiographic PD or death from any cause, whichever occurs first (per PCWG3 criteria). PFS6 is defined as the percentage of patients alive and progression-free at 6 months (26 weeks) after the first dose of CTT1403. Distributions for PFS, DoR, duration of complete response (DoCR), and OS will be estimated by Kaplan-Meier methodology.

The mean percent change from baseline on BPI will be descriptively reported for the study cohort.

Pharmacokinetics

PK parameters values that will be calculated to assess distribution and elimination half-life and reported as a mean +/- standard deviation.

Dosimetry

Organ dosimetry (primarily kidney and tumor is warranted) will be measured from SPECT/CT imaging at the timepoints listed above, following the first CTT1403 injection.

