**Duration of Treatment and Study Participation**

In the absence of treatment delays due to AEs, treatment be administered every 6 weeks, for up to 2 doses or until one of the following occurs:

1. Disease progression
2. Inter-current illness that prevents further administration of treatment
3. Unacceptable AE(s)
4. Patients decides to withdraw from the study
5. Significant patient non-compliance with protocol
6. General or specific changes in the patients' condition render the patient unacceptable for further treatment in the judgment of the investigator.
7. The patient has received 2 doses of CTT1403
8. A second dose of CTT1403 will not be given if the estimated cumulative kidney exposure exceeds 23Gy as determined by SPECT dosimetry following the first dose of CTT1403.

Following completion of treatment, patients will undergo EOT assessments 42 (+ 7) days after their last dose of study drug and will continue to be followed every 4 weeks up to 12 weeks and at 6 months post-treatment. Patients not exhibiting PD at the EOT assessment will be contacted every 90 days following final CTT1403 administration to report on disease progression for up to 6 months after last dose of study drug. Patients will undergo physical examination and lab donation of blood for assessment of CBC and creatinine every 4 weeks thereafter for 12 weeks after the last dose, until patient withdrawal from study, or death, whichever occurs first. Upon observation of delayed CBC recovery or other demonstration of drug related toxicity, the long-term observation period will be extended until recovery is observed and/or toxicities are resolved. Patients removed from study for unacceptable treatment related AEs will be followed until resolution or stabilization of all treatment related AEs Grade 2 or above.

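### The TEAE table by system organ class and preferred term stops 30 days after the last dose although adverse events are collected for 3 months, and the other safety summaries do not say which period they cover

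*Combined protocol and SAP*

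**What the plan says.** The safety part of Statistical Methods opens its adverse event analysis with a limit: "Treatment-emergent AEs (TEAEs) through 30 days after last dose of study drug will be summarized by MedDRA version 20.0 system organ class". This table also goes down to preferred term. The sentences that follow carry no limit:

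- How often each term occurs: "The incidences and percentages of patients experiencing each AE preferred term will be summarized with descriptive statistics"
- Severity and attribution: "Adverse events will also be summarized by NCI-CTCAE version 4.03 grade and by causality"
- Selected classes of event: "Dose-limiting toxicities, Grades 3 and 4 AEs, SAEs, and AEs resulting in dose modification or treatment discontinuation will be summarized by preferred terms"
- Laboratory results: "Incidences of laboratory abnormalities will be summarized with descriptive statistics"

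Of the displays named there, only DLTs have a period fixed elsewhere: Definition of Dose-Limiting Toxicity confines them to the 6-week Cycle 1.

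Collection runs longer. Safety Assessments states: "The AE-reporting period begins with the initiation of study drug and continues through 3 months after the last dose of study drug". It requires every event in that period to be reported whatever its attribution, and adds: "Any known untoward event that occurs beyond the AE-reporting period that the Investigator assesses as related to study drug should also be reported". The second of the two sections headed Duration of Treatment and Study Participation provides for "assessment of CBC and creatinine every 4 weeks thereafter for 12 weeks after the last dose" and lengthens observation if blood counts recover late or drug-related toxicity appears.

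Study Endpoints makes the adverse event profile by CTCAE a primary endpoint of the expansion period.

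**The concern.** The plan collects events, and schedules laboratory checks, well beyond the cut-off of the one table that it describes by system organ class and preferred term. Applied as written, the rule leaves an event with first onset between day 31 and month 3 out of that table, although it has been collected. The provisions on late blood count recovery and the limit on cumulative kidney exposure show that the protocol itself looks for delayed marrow and kidney effects.

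At stake is the clarity of a primary endpoint of the expansion. The grade summary is the closest counterpart to that endpoint, and its period is not stated. Two programmers could build different tables from the same text, and adverse event tables in one report could cover different periods without saying so. With at most 43 patients in a first-in-human study, a reader needs to know whether late-onset cytopenias or creatinine changes have been counted.

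**Working it through.** The plan gives no figure of its own to reproduce. The check compares the stated periods.

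**Inputs**

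- TEAE table: to 30 days after the last dose (Statistical Methods).
- Collection: to 3 months after the last dose (Safety Assessments). I take this as 90 days; calendar months give 89 to 92.
- Cycle length: 6 weeks, or 42 days, with dosing on Day 1 and at most two doses (Study Design).
- DLT period: Cycle 1, 42 days (Definition of Dose-Limiting Toxicity).
- Blood count and creatinine checks: every 4 weeks to 12 weeks after the last dose (Duration of Treatment and Study Participation, second section).
- EOT assessment: 42 (+7) days after the last dose in that section, but 30 (+7) days in the first section of the same name.

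**Share of the period after the last dose**

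- Outside the table: 90 − 30 = 60 days, and 60/90 = 67%.
- Range: 59/89 = 66% to 62/92 = 67%.

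**Share of the whole collection period, two doses without delay**

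- Length: 42 + 90 = 132 days.
- Outside the table: 60/132 = 45%. Range: 59/131 = 45% to 62/134 = 46%.
- A delayed second dose lengthens the denominator and lowers this share.

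**Cycle 1 for a patient given one dose**

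- With dosing on Day 1, 30 days later is Day 31, which is still inside the window.
- Days outside: Days 32 to 42, or 11 days, and 11/42 = 26%.
- A DLT with onset on those days counts in the DLT summary but not in the TEAE table. For a patient given two doses the window runs from the second dose, so all of Cycle 1 is inside.
- The plan foresees one-dose patients, for example when estimated cumulative kidney exposure exceeds 23 Gy.

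**Laboratory checks after day 30**

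- Counted from the last dose: days 28, 56 and 84. Two of the three fall after day 30.
- Counted from EOT at day 42 to 49: the first check is at 42 + 28 = 70 to 49 + 28 = 77. The next would be at day 98 to 105, beyond 12 weeks (84 days), so there is one check, and it is after day 30.
- Counted from EOT at day 30 to 37: the first check is at day 58 to 65, also after day 30.

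Each way of counting puts at least one check beyond the cut-off, but the number and timing depend on text that is not settled.

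**The case against.** A 30-day window for treatment-emergent events is ordinary, and it is not an error in itself. That stands.

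The strongest objection is that late events may already be covered. The 30-day limit is attached to TEAEs alone; the next sentences speak of adverse events without a limit, and Safety Assessments defines the reporting period as 3 months. On that reading the preferred-term, grade, causality, Grade 3-4 and SAE summaries would include days 31 to 90. The text permits this but does not settle it: the word *also* in the grade and causality sentence could equally carry the 30-day limit forward. So a reader who infers that late events will be missing from the report goes further than the documents allow. What they support is that such events are outside one table and that no other general summary is stated to include them.

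Other stronger inferences also fail:

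- That the TEAE table is the only adverse event display with a defined period. The DLT summary has one too, and for a one-dose patient it reaches past day 30, though only for events that qualify as DLTs and only to Day 42.
- That laboratory checks are fixed at weeks 8 and 12. This holds only if the 4-week intervals are counted from the last dose.
- That the 30-day cut was taken from the 30 (+7) day EOT timing. The documents do not say so.

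Late events are also harder to interpret, because progression and later therapy contribute to them. That stands as a caution, but the protocol already requires their collection regardless of attribution. Finally, the safety analysis is descriptive and the data are collected, so the matter can be put right in the analysis text.

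**Conclusion.** The point holds. The stated cut-off leaves about two thirds of the collection period after the last dose (about 45% of the whole period for an undelayed two-dose patient) outside the TEAE table. For a one-dose patient the excluded time includes the last 11 days of Cycle 1. The period covered by the remaining summaries, apart from DLTs, is unstated.

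This rests on taking 3 months as 90 days, on dosing on Day 1 and, for the 45%, on an undelayed second dose. A reader might take 67% as the share of events lost. The documents give no event rates or onset times, so no effect on incidence can be computed. Nor does the point touch DLT counts or escalation decisions, which rest on the 6-week window. It should be fixed before the safety tables are produced; it does not call the design into question.

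**What to change.** - Present the table by system organ class and preferred term through 3 months after the last dose, keeping the 30-day results as a separate column or split.
- State that the preferred-term incidence, grade, causality, Grade 3-4, SAE and laboratory summaries cover the same AE-reporting period, and that the DLT summary covers Cycle 1.
- List related events reported after the AE-reporting period, so that none is dropped.
- Reconcile the two EOT timings, 30 (+7) and 42 (+7) days, and state the day from which the 4-weekly laboratory checks are counted.

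The analysis changes need a few sentences, one extended table and one listing. They need no new visit, since the events are already collected. The price is interpretation. Late rates will include some events due to progression or later therapy, and they rest on less even follow-up: Study Design limits the 4-weekly visits to patients without progression who start no other therapy, while the later section on duration is broader. The split at day 30 makes this visible.

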CTT  
CTT1403 Phase 1

Name of Sponsor Cancer Targeted Technologies, Inc.
Name of Investigational Products CTT1403 –  Lu-PSMA targeting therapeutic agent CTT1057 –  F-PSMA targeting diagnostic agent, or  Ga-PSMA-11
Title of Study Phase 1 Dose Escalation/Expansion Study of CTT1403 in Patients with Metastatic Castration-Resistant Prostate Cancer (mCRPC).
Study Phase Phase 1
ClinicalTrials.gov Identifier NCT03822871
Study Center(s): University of California San Francisco
Principal Investigator Confidential
Date March 2, 2021
Study Objectives Primary Objectives Dose-Escalation Period 

• Determine the safety and tolerability of CTT1403.

• Determine the dose-limiting toxicity (DLT) and maximum tolerated dose (MTD) following a single dose

 Dose-Expansion Period 

• Determine the preliminary antitumor activity of CTT1403 in patients with mCRPC as measured by objective tumor response by Response Evaluation Criteria in Solid Tumors (RECIST) 1.1 in accordance with Prostate Cancer Working Group 3 (PCWG3) criteria.

 Secondary Objectives 

• Characterize the organ dosimetry and pharmacokinetics of CTT1403

• Determine the change from baseline in patient reported pain as assessed by Brief Pain Inventory (BPI)

Study Endpoints Primary Endpoints Dose-Escalation Period 

• Frequency of DLTs at escalating dose levels of CTT1403 during Cycle 1 (6-week period)

 Dose-Expansion Period 

• Objective response rate by RECIST 1.1

• Adverse event profile by CTCAE v5 criteria

 Secondary Endpoints 

• Assessment of PK (distribution and elimination t1/2)

• Assessment of organ dosimetry of CTT1403 by SPECT/CT imaging at various timepoints

• Change from baseline in patient reported pain as measured by Brief Pain Inventory (BPI)

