**Dose-Expansion Period**

A total of up to 10 patients will be treated at the MTD, or maximum tested dose (if no MTD is identified), or at a dose below the MTD (if there is evidence suggesting a favorable risk/benefit

profile) to provide further characterization of the safety, tolerability, PK, and pharmacodynamics of CTT1403.

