#### **Number of Patients (planned)**

A total of up to 43 patients will be enrolled, consisting of up to 33 patients during the dose-escalation period of the study, and approximately 10 patients during the dose-expansion period of the study, if this period is warranted.

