#### **Inclusion Criteria (Dose-Escalation and Dose-Expansion Periods)**

To be enrolled in the study, patients will be required to meet all of the following criteria:

1. Patients must have histologically confirmed prostate adenocarcinoma that is metastatic and castration resistant (mCRPC). Patients with de novo small cell carcinoma of the prostate are excluded from participation.
2. At least 3 metastatic foci avid for PSMA-specific PET agent (CTT1057) uptake on Screening PSMA PET. PSMA avidity is defined as  $SUV_{max} >$  mediastinal blood pool.
3. Has received docetaxel, ineligible for docetaxel, or refused docetaxel for the treatment of prostate cancer.
4. Has progression by the PCWG3 criteria during or after treatment with abiraterone, enzalutamide, and/or apalutamide.
5. Has serum testosterone  $< 50$  ng/dL during screening. Patients without a history of bilateral orchiectomy are required to remain on luteinizing hormone-releasing hormone (LHRH) analog during the course of protocol therapy.
6. Male Age  $\geq 18$  years.
7. Has Eastern Cooperative Oncology Group (ECOG) performance status of 0 or 1 (see Appendix 2).
8. Demonstrate adequate organ function as defined below:

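### The only planned summary of BPI pain is a mean percent change, which has no value at a zero baseline and can differ in sign from the mean change in score

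*Combined protocol and SAP*

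**What the plan says.** Under Study Objectives, the secondary pain objective reads "Determine the change from baseline in patient reported pain as assessed by Brief Pain Inventory (BPI". Under Study Endpoints, the matching secondary endpoint reads "Change from baseline in patient reported pain as measured by Brief Pain Inventory (BPI". Neither mentions percent.

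Statistical Methods (Efficacy) contains the only BPI analysis: "The mean percent change from baseline on BPI will be descriptively reported for the study cohort". It gives no formula for the percent change and does not say which BPI score is used. It plans no absolute change, median or measure of spread for BPI, and gives no rule for a baseline of zero.

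The inclusion list opens with "To be enrolled in the study, patients will be required to meet all of the following criteria". Neither that list nor the exclusion list sets a minimum pain score. Performance status is limited by "Has Eastern Cooperative Oncology Group (ECOG) performance status of 0 or 1".

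On size, Number of Patients (planned) states "A total of up to 43 patients will be enrolled", and the Dose-Expansion Period section states "A total of up to 10 patients will be treated at the MTD".

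**The concern.** A percent change divides by the patient's own baseline. When that baseline is small, a rise of one or two points becomes a very large percentage; when it is zero, there is no value. Nothing in the eligibility criteria keeps patients with little or no pain out of the study, so both situations can arise.

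The study has no control arm and attaches no test to pain, so this one figure is the whole pain result. If it can be undefined for eligible patients, or be driven by the few with the lowest baselines, it may describe the cohort's pain poorly. The two faults can also pull in opposite directions. Dropping patients at zero, who on the assumed scale can only stay the same or worsen, would flatter the result; small rises from low baselines would make it look worse. A reader could not undo either effect without the individual data.

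**Working it through.** The documents give no SD, effect size, power or sample-size figure for BPI, so there is no stated number to reproduce. The check compares the planned statistic with absolute change in the same patients.

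**Inputs from the documents:** the endpoint is a change from baseline; the planned summary is a mean percent change; there is no minimum baseline pain; there are up to 43 patients overall and up to 10 in expansion.

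**Assumptions, not in the documents:** pain is scored 0 to 10, 0 is no pain and lower is better; the planned statistic is the mean of individual percent changes; the share of patients at baseline zero is varied from 10% to 40%.

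**Formulas.** With baseline b and follow-up f, absolute change = f − b and percent change = 100 × (f − b)/b, which is undefined at b = 0.

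**Step 1: two patients**
- 1 to 3: change +2; percent change 100 × 2/1 = +200%.
- 8 to 4: change −4; percent change 100 × (−4)/8 = −50%.
- Mean change = (2 − 4)/2 = −1.0 point. Mean percent change = (200 − 50)/2 = +75%.

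**Step 2: ten illustrative patients**

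| Baseline | Follow-up | Change | Percent change |
|---|---|---|---|
| 8 | 5 | −3 | −37.5 |
| 7 | 4 | −3 | −42.9 |
| 6 | 4 | −2 | −33.3 |
| 6 | 4 | −2 | −33.3 |
| 5 | 3 | −2 | −40.0 |
| 4 | 3 | −1 | −25.0 |
| 2 | 3 | +1 | +50.0 |
| 1 | 3 | +2 | +200.0 |
| 1 | 2 | +1 | +100.0 |
| 0 | 1 | +1 | undefined |

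- All 10: the mean falls from 40/10 = 4.0 to 32/10 = 3.2, a mean change of −0.8.
- The 9 with a defined percent change: mean percent change = (350.0 − 212.0)/9 = +15.3%. The same 9 have a mean absolute change of −9/9 = −1.0 and a median percent change of −33.3%.

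**Step 3: how often a value would be undefined.** If a share p start at zero, the expected number is n × p and the chance of at least one is 1 − (1 − p)^n.

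| p | Expected, n = 10 | P(at least one), n = 10 | Expected, n = 43 | P(at least one), n = 43 |
|---|---|---|---|---|
| 10% | 1.0 | 65% | 4.3 | 99% |
| 20% | 2.0 | 89% | 8.6 | >99% |
| 30% | 3.0 | 97% | 12.9 | >99% |
| 40% | 4.0 | 99% | 17.2 | >99% |

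**Step 4: how often the sign would reverse.** The simulation used 20,000 trials per setting, with 10%, 20% or 30% of patients at zero and other baselines uniform on the integers 1 to 8. Follow-up was 75% of baseline plus noise with SD 1.5, rounded and kept within 0 to 10. Among trials whose mean change was an improvement in patients with a non-zero baseline, the mean percent change in those same patients was positive in about 11% at n = 10 and about 2% to 3% at n = 43.

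**The case against.** - **Percent change is itself a form of change from baseline.** The endpoint does not say absolute. A reader might infer that the analysis contradicts or replaces the endpoint; the documents do not support that. The analysis section can be read as choosing a metric that the endpoint left open. What stands is that the metric chosen is poorly behaved in this population.
- **The formula is not stated.** Percent change in the cohort mean is a possible reading. It gives 100 × (7 − 9)/9 = −22% for the two patients and 100 × (32 − 40)/40 = −20% for the ten, with the right sign and no patient undefined. This is fair, so the point depends on the usual reading; the text does not settle which is meant.
- **Exclusion of pain-free patients is not stated.** A reader might infer that they are silently dropped. The plan does not say so; it is silent on how they are handled.
- **Zero baselines are possible, not shown to be expected.** Entrants have progressive metastatic disease with at least three avid foci, and the documents give neither a baseline pain distribution nor the BPI scale. The 10% to 40% range is an assumption.
- **The two-patient example is chosen to show a reversal.** It should not be taken as the usual outcome. If the study cohort means all treated patients, the simulated frequency is only 2% to 3%.
- **Little depends on the result.** Pain is a descriptive secondary endpoint in an uncontrolled phase 1 study, and no escalation or stopping rule uses it. This limits the severity, but the figure is still the only pain result that the study plans to report.

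**Conclusion.** The point holds as a weakness in the chosen summary measure. On the usual reading, and on a scale where 0 is possible and lower is better, the plan can leave eligible patients without a value and gives no rule for them. It also lets low baselines dominate the mean, which can then show worsening while mean pain improves: +75% against −1.0 point in two patients, and +15.3% in nine patients against −0.8 point in all ten. The arithmetic shows that this can happen. Under the simulation's assumptions it happens in a minority of improving trials, about one in nine at 10 patients and far fewer at 43.

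The effect is confined to the description of one secondary endpoint. It does not touch the primary objectives or dose escalation. It is worth correcting because the remedy is almost free.

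**What to change.** In Statistical Methods (Efficacy), make absolute change from baseline in the BPI pain score the summary. Name the score used. At the scheduled BPI assessments, report the mean with SD, the median with range, and the number of patients contributing, for all patients with a baseline and a post-baseline value.

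If percent change is kept, make it supplementary: define it, limit it to patients with a baseline above zero, report the median, and state how many patients are excluded.

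The cost is a small change to the analysis text. Absolute change uses the same baseline and follow-up scores that percent change needs, so no new data, patients or visits are required.

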**Dose-Escalation Period**

It is estimated that up to 10 dose levels will be evaluated during the dose-escalation period of the study using an accelerated scheme for the first 3 doses (n=1/dose level), followed by a 3+3 dose escalation scheme for the final 7 doses. One patient will be enrolled at each of the first 3 dose levels. If a Grade  $\geq 2$  treatment-related AE is experienced during the DLT window of 6 weeks, then dose escalation schema will convert to a 3+3 design. Starting with enrollment of dose level 4, the study will convert to a 3+3 dose design, if not initiated sooner. All safety data from all patients enrolled in each cohort will be reviewed by the Data Safety Monitoring Committee (DSMB), with members minimally including the Principal Investigator and Sponsor, and sponsor Medical Monitor, to confirm any DLTs that were experienced, and to make a determination regarding enrollment in the next cohort. Based on the evaluation of the data, it may be decided that enrollment at an intermediate dose level or alternative dosing schedule not specified in the protocol will take place. If < 33% of patients (i.e., 0 of 1 (dose level 1-3) or 0 of 3 (dose level 4-10), 1 of 6 patients (all dose levels requiring additional enrollment) within a cohort have a DLT within the DLT window, then enrollment of the next cohort may commence with approval from the Medical Monitor. If  $\geq 33\%$  of the patients ( $\geq 2$  of up to 6 patients) within a cohort experience a DLT in the DLT window, then the MTD will have been exceeded and the previous dose level will be considered the MTD.

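### The half-life summary (mean and SD) has no stated grouping: by dose level it gives no SD at the three planned one-patient levels, and pooled it would mask a dose trend

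*Combined protocol and SAP*

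**What the plan says.** All references are to the combined protocol and SAP.

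- **Objective and endpoint.** Study Objectives lists as a secondary objective: "Characterize the organ dosimetry and pharmacokinetics of CTT1403". Study Endpoints narrows the PK part to the distribution and elimination half-lives.
- **Analysis.** Statistical Methods, Pharmacokinetics, is a single sentence. The half-lives are to be "reported as a mean +/- standard deviation". It gives no grouping, individual listing, median, range, geometric summary or examination of dose.
- **Patients per level.** Dose-Escalation Period: "One patient will be enrolled at each of the first 3 dose levels", "followed by a 3+3 dose escalation scheme for the final 7 doses". A related Grade 2 or higher AE in the DLT window changes this at the early levels: "then dose escalation schema will convert to a 3+3 design".
- **Activities.** The dose table in Study Design runs from 0.75 GBq at level 1 to 13.5 GBq at level 10.
- **Sampling.** Study Design, and Pharmacokinetic and Dosimetry Assessments, have PK blood drawn from every escalation patient. Number of Patients (planned) allows up to 33 of them.

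**The concern.** The sentence can be carried out in two ways, and each loses something. Reported by level, the SD is missing at the three lowest activities and barely informative at the others. Reported as one pooled figure, any change of half-life with activity is folded into the SD and looks like ordinary between-patient spread.

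A second, weaker issue is the choice of the arithmetic mean. Half-life is a positive quantity. If its distribution is right-skewed, the arithmetic mean lies above the value of a typical patient.

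At stake is how well a stated secondary objective is met in a first-in-human study. The escalation data contain some information on whether half-life varies with activity, and the planned summary does not extract it.

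**Working it through.** The plan gives no precision or power figure for PK, so there is nothing of its own to reproduce. The documents give no CV for half-life either, so every CV below is an assumption.

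**Activity range.** 13.5 / 0.75 = 18-fold, if all ten levels are reached.

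**SD by level.** The sample SD divides by n − 1, which is 0 at n = 1, so it is undefined. For normal data the 95% limits are the observed SD times √[(n − 1)/χ²].
- n = 3: √(2/7.378) = 0.52 to √(2/0.0506) = 6.3.
- n = 6: √(5/12.83) = 0.62 to √(5/0.831) = 2.5.

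**Pooled SD.** Take one patient at each of levels 1 to 3 and three at each of levels 4 to 10: 3 + 21 = 24 patients. With x = ln(nominal activity), Sxx = Σ(x − x̄)² = 12.78, so the variance of x is 12.78/24 = 0.533. Let half-life vary as activity to the power b. With 30% within-level CV the log-scale variance is ln(1 + 0.3²) = 0.0862, and the apparent pooled CV is √[exp(0.0862 + 0.533b²) − 1].

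| b | Change in half-life over 18-fold | Apparent pooled CV |
|---|---|---|
| 0 | none | 30% |
| 0.20 | 18^0.20 = 1.8-fold | 34% |
| 0.24 | 2.0-fold | 35% |
| 0.30 | 2.4-fold | 38% |

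Nobody reading a pooled CV of 34% or 35% would infer a near-doubling across the range.

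**Arithmetic against geometric mean.** Under log-normality the ratio is √(1 + CV²): 1.02 at 20%, 1.044 at 30%, 1.118 at 50%, 1.41 at 100%.

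**What a regression would give.** For log half-life on x, the slope SE is √[ln(1 + CV²)]/√Sxx. A doubling over 18-fold is a slope of ln 2/ln 18 = 0.693/2.890 = 0.240. Power is for a two-sided 5% t-test with N − 2 degrees of freedom at that slope.

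| Escalation reaches | N | Sxx | CV | Slope SE | 95% CI half-width | 0.240/SE | Power |
|---|---|---|---|---|---|---|---|
| Level 10 | 24 | 12.78 | 30% | 0.082 | 0.17 | 2.9 | 80% |
| Level 10 | 24 | 12.78 | 50% | 0.132 | 0.27 | 1.8 | 41% |
| Level 7 | 15 | 6.18 | 30% | 0.118 | 0.26 | 2.0 | 47% |
| Level 6 | 12 | 4.45 | 30% | 0.139 | 0.31 | 1.7 | 34% |

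With all ten levels, the three single patients contribute (4.09 + 1.77 + 1.08)/12.78 = 54% of Sxx, and the level 1 patient alone 4.09/12.78 = 32%. The slope therefore leans on unreplicated values.

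**The case against.** Most of the opposing case has force.

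- **The two grouping objections are alternatives.** The missing SD arises only in a by-level summary, and the masked trend only in a pooled one. A reader might infer that the planned summary suffers from both at once. The text does not support that; what is certain is that the grouping is not stated.
- **Only is inferred from silence.** The plan does not exclude listings or further summaries, and because every escalation patient is sampled, individual values can still be tabulated later. That stands, but this is the only PK analysis specified in advance.
- **The one-patient limb is modest.** At n = 1 the mean is simply the value, no summary can add to it, and a level converted to 3+3 no longer has n = 1. A geometric CV at n = 3 is as unstable as an SD. Listing the individual values is what helps there.
- **Skewness is assumed.** At 20% to 30% CV the effect is only 2% to 4%. That mean minus 2 SD can fall below zero at high CV is not an error in the plan, which proposes no such interval.
- **The regression is an addition.** The endpoint asks for half-lives, not for their relation to dose. A reader might also infer that the escalation data would usually reveal a doubling. That needs all ten levels filled and a CV near 30%; the plan speaks of up to ten levels and stops once the MTD is exceeded.

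What survives is that neither way of carrying out the sentence serves the objective well, and that a better summary is available from data already being collected.

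**Conclusion.** The point holds as a low-cost improvement. The half-life summary lacks a stated grouping. By level, it yields no SD at the three planned one-patient levels and a very imprecise one at n = 3. Pooled over up to 18-fold, it would hide a near-doubling behind a rise in CV of 4 to 5 percentage points. These findings do not depend on skewness. The pooled figures assume 30% within-level CV, a power relation between half-life and activity, and 24 patients over all ten levels. The overstatement by the arithmetic mean, about 4% at 30% CV and 12% at 50% CV, depends on log-normality and is secondary.

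It would be tempting to conclude that dose decisions are at risk. The documents do not support that: escalation runs on DLTs, the limit on a second dose uses SPECT kidney dosimetry, and no rule uses plasma half-life. The effect is confined to the quality of a descriptive secondary endpoint.

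**What to change.** Replace the PK sentence in Statistical Methods with a plan along these lines:

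1. List both half-lives for every escalation patient, with dose level and measured administered activity.
2. Give the geometric mean and geometric CV (or median and range) by dose level where n is at least 3, and overall, labelling each summary with its grouping.
3. Fit a descriptive regression of log half-life on log measured administered activity over all escalation patients. Report the slope with its 95% CI as estimation, without a test and without any statement that a trend would be detected. State alongside it how many patients the lowest levels contribute.

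Use measured activity as the covariate, which also accommodates any intermediate dose level. The dose table's GBq and mCi figures disagree at levels 2 and 4: 45/1.5 = 30 and 67.6/3.0 = 22.5 mCi per GBq, against 54.1/2.0 = 27 at level 3. These entries must be reconciled before any dose-related analysis. The 18-fold ratio is unaffected.

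The cost is SAP wording and a few lines of code, with no new samples or patients. The drawback is a slope that rests heavily on the single-patient levels and has a wide interval if escalation ends early; the CI will show this openly.
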